**Surgical and medical procedures**

Adverse Event	Grade				
	1	2	3	4	5
Surgical and medical procedures - Other, specify	Asymptomatic or mild symptoms; clinical or diagnostic observations only; intervention not indicated	Moderate; minimal, local or noninvasive intervention indicated; limiting age-appropriate instrumental ADL	Severe or medically significant but not immediately life-threatening; hospitalization or prolongation of existing hospitalization indicated; disabling; limiting self care ADL	Life-threatening consequences; urgent intervention indicated	Death

Vascular disorders					
Adverse Event	Grade				
	1	2	3	4	5
Capillary leak syndrome	-	Symptomatic; medical intervention indicated	Severe symptoms; intervention indicated	Life-threatening consequences; urgent intervention indicated	Death
Definition: A disorder characterized by leakage of intravascular fluids into the extravascular space. This syndrome is observed in patients who demonstrate a state of generalized leaky capillaries following shock syndromes, low-flow states, ischemia-reperfusion injuries, toxemias, medications, or poisoning. It can lead to generalized edema and multiple organ failure.					
Flushing	Asymptomatic; clinical or diagnostic observations only; intervention not indicated	Moderate symptoms; medical intervention indicated; limiting instrumental ADL	Symptomatic, associated with hypotension and/or tachycardia; limiting self care ADL	-	-
Definition: A disorder characterized by episodic reddening of the face.					
Hematoma	Mild symptoms; intervention not indicated	Minimally invasive evacuation or aspiration indicated	Transfusion, radiologic, endoscopic, or elective operative intervention indicated	Life-threatening consequences; urgent intervention indicated	Death
Definition: A disorder characterized by a localized collection of blood, usually clotted, in an organ, space, or tissue, due to a break in the wall of a blood vessel.					
Hot flashes	Mild symptoms; intervention not indicated	Moderate symptoms; limiting instrumental ADL	Severe symptoms; limiting self care ADL	-	-
Definition: A disorder characterized by an uncomfortable and temporary sensation of intense body warmth, flushing, sometimes accompanied by sweating upon cooling.					
Hypertension	Prehypertension (systolic BP 120 - 139 mm Hg or diastolic BP 80 - 89 mm Hg)	Stage 1 hypertension (systolic BP 140 - 159 mm Hg or diastolic BP 90 - 99 mm Hg); medical intervention indicated; recurrent or persistent (>=24 hrs); symptomatic increase by >20 mm Hg (diastolic) or to >140/90 mm Hg if previously WNL; monotherapy indicated Pediatric: recurrent or persistent (>=24 hrs) BP >ULN; monotherapy indicated	Stage 2 hypertension (systolic BP >=160 mm Hg or diastolic BP >=100 mm Hg); medical intervention indicated; more than one drug or more intensive therapy than previously used indicated Pediatric: Same as adult	Life-threatening consequences (e.g., malignant hypertension, transient or permanent neurologic deficit, hypertensive crisis); urgent intervention indicated Pediatric: Same as adult	Death
Definition: A disorder characterized by a pathological increase in blood pressure; a repeatedly elevation in the blood pressure exceeding 140 over 90 mm Hg.					
Hypotension	Asymptomatic, intervention not indicated	Non-urgent medical intervention indicated	Medical intervention or hospitalization indicated	Life-threatening and urgent intervention indicated	Death
Definition: A disorder characterized by a blood pressure that is below the normal expected for an individual in a given environment.					
Lymph leakage	-	Symptomatic; medical intervention indicated	Severe symptoms; radiologic, endoscopic or elective operative intervention indicated	Life-threatening consequences; urgent intervention indicated	Death
Definition: A disorder characterized by the loss of lymph fluid into the surrounding tissue or body cavity.					
Lymphedema	Trace thickening or faint discoloration	Marked discoloration; leathery skin texture; papillary formation; limiting instrumental ADL	Severe symptoms; limiting self care ADL	-	-
Definition: A disorder characterized by excessive fluid collection in tissues that causes swelling.					
Lymphocele	Asymptomatic; clinical or diagnostic observations only; intervention not indicated	Symptomatic; medical intervention indicated	Severe symptoms; radiologic, endoscopic or elective operative intervention indicated	-	-
Definition: A disorder characterized by a cystic lesion containing lymph.					
Peripheral ischemia	-	Brief (<24 hrs) episode of ischemia managed non-surgically and without permanent deficit	Recurring or prolonged (>=24 hrs) and/or invasive intervention indicated	Life-threatening consequences; evidence of end organ damage; urgent operative intervention indicated	Death
Definition: A disorder characterized by impaired circulation to an extremity.					
Phlebitis	-	Present	-	-	-
Definition: A disorder characterized by inflammation of the wall of a vein.					
Superficial thrombophlebitis	-	Present	-	-	-
Definition: A disorder characterized by a blood clot and inflammation involving a superficial vein of the extremities.					

Vascular disorders					
Adverse Event	Grade				
	1	2	3	4	5
Superior vena cava syndrome	Asymptomatic; incidental finding of SVC thrombosis	Symptomatic; medical intervention indicated (e.g., anticoagulation, radiation or chemotherapy)	Severe symptoms; multi-modality intervention indicated (e.g., anticoagulation, chemotherapy, radiation, stenting)	Life-threatening consequences; urgent multi-modality intervention indicated (e.g., lysis, thrombectomy, surgery)	Death
Definition: A disorder characterized by obstruction of the blood flow in the superior vena cava. Signs and symptoms include swelling and cyanosis of the face, neck, and upper arms, cough, orthopnea and headache.					
Thromboembolic event	Venous thrombosis (e.g., superficial thrombosis)	Venous thrombosis (e.g., uncomplicated deep vein thrombosis), medical intervention indicated	Thrombosis (e.g., uncomplicated pulmonary embolism [venous], non-embolic cardiac mural [arterial] thrombus), medical intervention indicated	Life-threatening (e.g., pulmonary embolism, cerebrovascular event, arterial insufficiency); hemodynamic or neurologic instability; urgent intervention indicated	Death
Definition: A disorder characterized by occlusion of a vessel by a thrombus that has migrated from a distal site via the blood stream.					
Vasculitis	Asymptomatic, intervention not indicated	Moderate symptoms, medical intervention indicated	Severe symptoms, medical intervention indicated (e.g., steroids)	Life-threatening; evidence of peripheral or visceral ischemia; urgent intervention indicated	Death
Definition: A disorder characterized by inflammation involving the wall of a vessel.					
Visceral arterial ischemia	-	Brief (<24 hrs) episode of ischemia managed medically and without permanent deficit	Prolonged (>=24 hrs) or recurring symptoms and/or invasive intervention indicated	Life-threatening consequences; evidence of end organ damage; urgent operative intervention indicated	Death
Definition: A disorder characterized by a decrease in blood supply due to narrowing or blockage of a visceral (mesenteric) artery.					
Vascular disorders - Other, specify	Asymptomatic or mild symptoms; clinical or diagnostic observations only; intervention not indicated	Moderate; minimal, local or noninvasive intervention indicated; limiting age-appropriate instrumental ADL	Severe or medically significant but not immediately life-threatening; hospitalization or prolongation of existing hospitalization indicated; disabling; limiting self care ADL	Life-threatening consequences; urgent intervention indicated	Death

**13.5 Appendix 5: Acute Radiation Morbidity Scoring Criteria (RTOG)**

	[ 0 ]	[ 1 ]	[ 2 ]	[ 3 ]	[ 4 ]
SKIN	No change over baseline	Follicular, faint or dull erythema/ epilation/dry desquamation/ decreased sweating	Tender or bright erythema, patchy moist desquamation/ moderate edema	Confluent, moist desquamation other than skin folds, pitting edema	Ulceration, hemorrhage, necrosis
UPPER G.I.	No change	Anorexia with <=5% weight loss from pretreatment baseline/ nausea not requiring antiemetics/ abdominal discomfort not requiring parasympatholytic drugs or analgesics	Anorexia with <=15% weight loss from pretreatment baseline/nausea &/ or vomiting requiring antiemetics/ abdominal pain requiring analgesics	Anorexia with >15% weight loss from pretreatment baseline or requiring N-G tube or parenteral support. Nausea &/or vomiting requiring tube or parenteral support/abdominal pain, severe despite medication/hematemesis or melena/ abdominal distention (flat plate radiograph demonstrates distended bowel loops)	Ileus, subacute or acute obstruction, perforation, GI bleeding requiring transfusion/abdominal pain requiring tube decompression or bowel diversion
LOWER G.I. INCLUDING PELVIS	No change	Increased frequency or change in quality of bowel habits not requiring medication/ rectal discomfort not requiring analgesics	Diarrhea requiring parasympatholytic drugs (e.g., Lomotil)/ mucous discharge not necessitating sanitary pads/ rectal or abdominal pain requiring analgesics	Diarrhea requiring parenteral support/ severe mucous or blood discharge necessitating sanitary pads/abdominal distention (flat plate radiograph demonstrates distended bowel loops)	Acute or subacute obstruction, fistula or perforation; GI bleeding requiring transfusion; abdominal pain or tenesmus requiring tube decompression or bowel diversion

	[ 0 ]	[ 1 ]	[ 2 ]	[ 3 ]	[ 4 ]
GENITOURINARY	No change	Frequency of urination or nocturia twice pretreatment habit/ dysuria, urgency not requiring medication	Frequency of urination or nocturia which is less frequent than every hour. Dysuria, urgency, bladder spasm requiring local anesthetic (e.g., Pyridium)	Frequency with urgency and nocturia hourly or more frequently/ dysuria, pelvis pain or bladder spasm requiring regular, frequent narcotic/gross hematuria with/ without clot passage	Hematuria requiring transfusion/ acute bladder obstruction not secondary to clot passage, ulceration or necrosis
HEMATOLOGIC WBC (X 1000)	$\geq 4.0$	3.0 - $<4.0$	2.0 - $<3.0$	1.0 - $<2.0$	$<1.0$
PLATELETS (X 1000)	$\geq 100$	75 - $<100$	50 - $<75$	25 - $<50$	$<25$ or spontaneous bleeding
NEUTROPHILS	$\geq 1.9$	1.5 - $<1.9$	1.0 - $<1.5$	0.5 - $<1.0$	$<0.5$ or sepsis
HEMOGLOBIN (GM %)	$>11$	11-9.5	$<9.5$ - 7.5	$<7.5$ - 5.0	-----
HEMATOCRIT (%)	$\geq 32$	28 - $<32$	$<28$	Packed RBC transfusion required	-----

GUIDELINES: The acute morbidity criteria are used to score/grade toxicity from radiation therapy. The criteria are relevant from day 1, the commencement of therapy, through day 90.

The evaluator must attempt to discriminate between disease- and treatment-related signs and symptoms.

An accurate baseline evaluation prior to commencement of therapy is necessary.

All toxicities Grade 3, 4 or 5\* must be verified by the Principal Investigator.

\*ANY TOXICITY WHICH CAUSED DEATH IS GRADED 5.

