- m Chemo/RT effects to be assessed at screening if subject is screened during chemoradiation
- n PET/CT to include standard uptake volume, must be performed within 4 weeks prior to Day 0
- o All labs for Day 0 and those associated with any treatment visit should be available prior to treatment and collected no more than 48 hours prior to treatment
- p PET/CT will be performed 3-4 months after Day 0
- q Not required at study discharge if performed at wk 32
- r Immune competence will be evaluated longitudinally throughout the study from the time of screening visit. No additional blood collection required.

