### **Primary Safety Endpoints:**

1. Incidence of adverse events (all, severe [graded per CTCAE v4.03], unexpected, serious) classified by system organ class (SOC), preferred term, severity, and relationship to study medication and schedule
2. Injection site reactions including pain, tenderness, erythema and induration at administration site
3. Rates of acute gastrointestinal, genitourinary, or other chemoradiation side effects above the expected, graded per Acute Radiation Morbidity Scoring Criteria (RTOG)
4. Changes in laboratory parameters from baseline

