### 6.1 Procedure by Visit

#### 6.1.1 Screening Evaluations

Subjects who consent to participate in the study will be eligible for screening and will have a tumor biopsy sample (i.e. unstained slides) sent to laboratory for HPV assessment that will be done either by ISH or PCR. If a subject has documented evidence of HPV-16 and/or HPV-18 infection results from cervical specimen obtained prior to anti-cancer treatment, then those results will be acceptable. If applicable, ThinPrep™ sample should also be sent simultaneously to the central lab for HPV assessment by PCR. Another cervical biopsy should be collected at screening if residual tissue is not available for additional assessment. The screening assessments, if required may be done in two parts. The first part will consist of consenting the subject and collecting cervical biopsy samples for HPV assessment. The second part of the visit will consist of performing the remaining screening assessment.

Subjects in Cohort 1 can be screened either prior to initiation of chemoradiation or during chemoradiation. Subjects should be screened and enrolled such that their first study treatment (Day 0) will be delivered within 2 weeks of completing their chemoradiation therapy.

Subjects in Cohort 2 can be screened at any time prior to the date of their first study treatment. Subjects should be screened and enrolled such that their first study treatment (Day 0) is no sooner than 2 weeks and no later than 4 weeks after completing the salvage therapy.

The following evaluations will be performed at **screening** visit prior to Day 0:

- Signed informed consent
- Histologic diagnosis of cervical cancer
- Collect demographic information
- Determination of eligibility per inclusion and exclusion criteria
- Medical and CIN/cancer history
- Medical/clinical assessment
- Adverse event (AE)/Serious adverse event (SAE) assessment
- Determine disease status
- Concomitant medications review
- Assessment of systemic reaction/toxicity/side effects of standard (chemoradiation) therapy (only if subject is screened during chemoradiation therapy)

- Full physical exam to include complete gynecological exam and ECOG performance status
- Vital Signs (including body temperature, respiratory rate, blood pressure, heart rate and height/weight)
- 12-lead ECG
- HPV assessment
- Tumor biopsy collection (required only if residual tissue or unstained slides are not available at screening)
- ThinPrep™ sample for HPV testing (if applicable)

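### Primary safety endpoint 3 is graded on the RTOG acute scale, but no subject has a required RTOG assessment before therapy, and some post-dose scores can fall after the scale's day-90 limit

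*Combined protocol and SAP*

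**What the plan says.** Section 3 lists as the third primary safety endpoint "Rates of acute gastrointestinal, genitourinary, or other chemoradiation side effects above the expected", graded on the RTOG scale in Appendix 5. The guidelines under that scale set two conditions: "An accurate baseline evaluation prior to commencement of therapy is necessary", and "The criteria are relevant from day 1, the commencement of therapy, through day 90". Some grades are written against the pre-radiation state, for example "Anorexia with <=5% weight loss from pretreatment baseline" and "Frequency of urination or nocturia twice pretreatment habit".

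Cohort 1 may be screened before or during chemoradiation (Section 6.1.1). Table 1 footnote m reads: "Chemo/RT effects to be assessed at screening if subject is screened during chemoradiation". Section 6.1.1 repeats the restriction: "only if subject is screened during chemoradiation therapy". The first RTOG assessment required of everyone is the pre-dose one on Day 0 (Section 6.1.2).

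After dosing, Table 1 schedules the assessment at Weeks 2 and 4, and Section 9.3.1 ends chemoradiation-toxicity reporting at Week 4. Section 6.1.2 also lists it at Weeks 6, 10 and 14.

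**The concern.** Footnote m works against the scale it serves. The women in whom a pre-radiation state can be observed directly are those screened before chemoradiation, and they are the ones for whom the screening assessment is not required. Women screened during chemoradiation are scored at screening, but after therapy has begun.

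The endpoint compares observed rates with those expected from standard therapy, so the reference state matters. If a site grades against the condition at Day 0, radiation symptoms already present may be missed. If it uses no reference, bowel or urinary symptoms caused by the tumor may be counted as toxicity. Appendix 5 asks the evaluator to separate disease from treatment effects, which is hard without a record of the starting state. Scores taken after day 90 apply an acute scale outside the period for which it is described.

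**Working it through.** The plan gives no figure on this point, so there is none to reproduce. The check has three parts.

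**1. Who has a required pre-therapy RTOG assessment?**

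- Cohort 1, screened before chemoradiation: none required at screening; first score on Day 0, after radiation.
- Cohort 1, screened during chemoradiation: scored at screening, with therapy already under way.
- Cohort 2: no assessment before salvage therapy is required. Salvage may be chemotherapy alone, and a woman with no remaining options may enter without recent therapy, so the start of therapy is not always defined.

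No group has one.

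**2. What does screening collect, and which grades need more?** Sections 6.1.1 and 6.2.3 require medical and cancer history, full and gynecological examination, weight, blood count, chemistry and adverse-event review. For a woman screened before chemoradiation, this supplies the weight and blood-count references. Bowel habit and urinary frequency or nocturia are not specified. In Appendix 5, the items that depend on baseline are mainly grade 0 versus 1, genitourinary grade 1, and the weight-loss percentages in upper GI grades 1 to 3. Most other grade 2 to 4 criteria are absolute: need for drugs, parenteral support or transfusion, gross hematuria, numeric blood counts.

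**3. When do the scores fall relative to day 90?** Let D be the length of the course in days, g the gap from its end to Day 0, and w the study week:

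radiation day of visit = D + g + 7w

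Inputs: D is at most 70 (10 weeks, Section 3). Appendix 3 gives 8 weeks as the limit for total radiation time with low-dose-rate brachytherapy. Section 1.4.2 describes external beam over 5 to 6 weeks followed by brachytherapy, so a 6-week total is shown as an assumed short course. The gap g is 0 to 14 days (Section 4.1).

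| Course | Gap (days) | Day 0 | Week 2 | Week 4 | Past day 90, Table 1 list | Past day 90, Section 6.1.2 list |
|---|---|---|---|---|---|---|
| 6 weeks | 0 / 7 / 14 | 42 / 49 / 56 | 56 / 63 / 70 | 70 / 77 / 84 | 0 / 0 / 0 of 2 | 2 / 3 / 3 of 5 |
| 8 weeks | 0 / 7 / 14 | 56 / 63 / 70 | 70 / 77 / 84 | 84 / 91 / 98 | 0 / 1 / 1 of 2 | 3 / 4 / 4 of 5 |
| 10 weeks | 0 / 7 / 14 | 70 / 77 / 84 | 84 / 91 / 98 | 98 / 105 / 112 | 1 / 2 / 2 of 2 | 4 / 5 / 5 of 5 |

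The Section 6.1.2 list is Weeks 2, 4, 6, 10 and 14. The thresholds for Day 0 are:

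- Week 4 passes day 90 if D + g > 90 − 28 = 62.
- Week 2 passes day 90 if D + g > 90 − 14 = 76.
- The latest permitted Day 0 is 70 + 14 = 84.

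The one-week visit window can move any single visit by 7 days.

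**The case against.** The best defense is that Appendix 5 asks for a baseline evaluation, not a baseline score. A form completed before radiation would show mostly zeros on the non-hematologic rows, and a pre-chemoradiation screening visit already records history, examination, weight and counts. The Day 0 score, required of everyone, is the natural reference for a change after INO-3112. The severe grades are largely absolute, adverse events other than chemoradiation toxicity are followed under CTCAE to the end of the study, and the analysis is descriptive.

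Much of this stands. A reader might infer that there is no pre-therapy visit or no baseline data at all; Section 6.1.1 shows otherwise for women screened beforehand. A reader might also infer that GI and GU rates will be graded too low throughout. The documents do not support that: most grade 2 to 4 criteria do not use baseline, the scale itself points to the pretreatment state, and the error could go either way.

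Three things remain. Bowel and urinary habit, which anchor the low grades in the two organ systems the endpoint names, are not required. Women screened during chemoradiation have no pre-therapy study visit. And Day 0 is a baseline for INO-3112, not for radiation, although Section 9.3.1 starts chemoradiation-toxicity reporting when chemoradiation begins.

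**Conclusion.** The screening rule conflicts with the scale's own requirement: no subject has a required RTOG score before therapy. The consequence is limited to the low and weight-based grades and to separating tumor symptoms from toxicity. Its direction cannot be stated in advance. With about 10 subjects, one regraded woman moves a rate by 1/10, or 10 percentage points.

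On timing, some post-dose scores fall after day 90. A reader might infer that most or all do. Under Table 1 and Section 9.3.1, both do only when Day 0 falls on radiation days 77 to 84, and neither does with a 6-week course. More scores fall late under the Section 6.1.2 list, but that list conflicts with Table 1 and Section 9.3.1. These results assume courses of 6 to 10 weeks and visits on their nominal dates. Cohort 2 women without a recent radiation start cannot be placed in the window. The change is worth making because a primary endpoint is affected and the remedy is small.

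**What to change.** Amend footnote m and the matching bullet in Section 6.1.1 so that the RTOG form, including bowel habit and urinary frequency and nocturia, is completed at screening for every woman screened before chemoradiation. For women screened during chemoradiation, and for Cohort 2 women whose salvage therapy included radiation, enter pretreatment values from the medical record or the Section 6.2.3 history and flag them as retrospective. State that later RTOG items are graded against these values.

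Record the radiation start date on the CRF and tabulate RTOG scores after day 90 separately. For Cohort 2 women without recent radiation, report these symptoms under CTCAE only, and define recent. Reconcile the Section 6.1.2 visit list with Table 1 and Section 9.3.1.

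The cost is one extra CRF page, at a visit that already takes place. The drawback is that baselines for some women will rest on recall or records.

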### **13.6 Appendix 6: Preparation of Investigational Products**

VGX-3100 and INO-9012 will be combined by the site pharmacist into a single syringe for subjects using the following procedure:

0. Using aseptic technique, withdraw 1.2 mL from the vial SynCon™ VGX-3100 with a 3 mL syringe and inject into an empty sterile vial. Set this “mixing” vial which now contains 1.2 mL of VGX-3100 aside.
1. Using a new 1 mL syringe, withdraw 0.12 mL from the vial SynCon™ INO-9012 and add the 0.12 mL to the “mixing” vial containing 1.2 mL of VGX-3100. The final volume of this vial should now be 1.32 mL of INO-3112(VGX-3100 / INO-9012).
2. Using a 3 mL syringe, withdraw 1.1 mL of INO-3112 from the “mixing” vial. This syringe will be used for dosing of subjects.

### 13.8 Appendix 8: New York Heart Association (NYHA) Functional Classification

The NYHA classifies heart failure into classes based on functional limitations and severity.

Class	Patient Symptoms
Class I (Mild)	No limitation of physical activity. Ordinary physical activity does not cause undue fatigue, palpitation, or dyspnea (shortness of breath).
Class II (Mild)	Slight limitation of physical activity. Comfortable at rest, but ordinary physical activity results in fatigue, palpitation, or dyspnea.
Class III (Moderate)	Marked limitation of physical activity. Comfortable at rest, but less than ordinary activity causes fatigue, palpitation, or dyspnea.
Class IV (Severe)	Unable to carry out any physical activity without discomfort. Symptoms of cardiac insufficiency at rest. If any physical activity is undertaken, discomfort is increased.

\*The Criteria Committee of the New York Heart Association. *Nomenclature and Criteria for Diagnosis of Diseases of the Heart and Great Vessels*. 9th ed. Boston, Mass: Little, Brown & Co; 1994:253-256.

